5.4.3 Loss to follow-up

For study purposes, patients will be considered lost to follow-up if any time-based assessment is missed and the corresponding data have not been received by the CC research staff after making additional follow-up attempts with the patient and/or HCP using all contact methods available (e.g., phone, app-based notifications). At least 3 attempts will

be made up to 4 months after the expected date of the missed assessment. The patient's eCRF will be re-opened if additional information is later obtained. All secondary contacts will also be contacted prior to considering a patient lost to follow-up. All data collected prior to the patient being lost to follow-up will be used for analyses, if possible. For analysis purposes, the date of study discontinuation will be recorded as the date of last contact.

Registry awareness, recruitment, and retention strategies to maximize enrollment and minimize loss to follow-up are described in Section 5.4.5.

5.4.4 External comparator cohorts

External comparators can provide additional context for study results and will be used to descriptively characterize study results, with MACDP report serving as the primary external comparator and EUROCAT serving as the secondary external comparator. These populations will represent the estimated underlying prevalence of major structural or genetic birth defects in the general US and EEA populations, respectively. Only aggregate, population-level data or published reports will be used for description.

5.4.4.1 Metropolitan Atlanta Congenital Defects Program

The MACDP, a population-based tracking system for birth defects (established in 1967) in the US, currently captures approximately 35,000 births per year from 3 metropolitan counties in the Atlanta area [CDC 2021]. MACDP has monitored trends in birth defects rates and has served as a case registry for descriptive, risk factor, and prognostic studies of birth defects. Since 1998, MACDP surveillance has required that any signs or symptoms of a defect in the child be reported before their sixth birthday. In a 2007 report, the MACDP presented data on the prevalence and descriptive characteristics of birth defects, including 67 individual defects, in metropolitan Atlanta, Georgia from 1968 to 2003 [Correa 2007].

Major structural or genetic birth defects affected approximately 3% of births in the US [CDC 2008]. The prevalence estimates of stillbirth in 2006 and 2008 using MACDP data were 8.0 (95% CI: 7.3–8.7) and 7.6 (95% CI: 6.9–8.4) per 1000 live births plus stillbirths [Duke 2014].

5.4.4.2 European Surveillance of Congenital Anomalies

EUROCAT is a European network of population-based registries for the epidemiologic surveillance of congenital anomalies [EC 2022]. Started in 1979, the registry includes over 1.7 million births surveyed annually in Europe from 43 registries in 23 countries. Approximately 29% of the European birth population is covered by this network.

A study using 13 registries from EUROCAT from 1 January 1998 through 31 December 2011, found an overall prevalence of congenital anomaly of 27.3 per 1000 births (range: 19.1–39.3 per 1000 births) [Groen 2017]. Of the 84,387 pregnancies with a known outcome (99.4%), 2.33% pregnancies were stillbirths. The proportion of early neonatal mortality (within 7 days of birth) was 2.37% and the proportion of late neonatal mortality (between 7 days to 27 days of life) was 0.84%.

5.4.4.3 Other potential sources

At the time of final report generation, any existing publicly available data sources (e.g., registries, cohorts) or published study results pertaining to insomnia treatment exposures during pregnancy will be reviewed and considered for a summary of results in addition to this registry, where feasible. No statistical comparisons will be made.

5.4.5 Registry awareness, recruitment, and retention

HCPs who treat patients with insomnia, including investigators involved in the clinical trial with OUVIVIO, will be informed of the pregnancy registry and asked to refer any patient who becomes pregnant to the registry CC or study website. When local regulations permit, patients will be able to enroll in the study through the app associated with the study website. Patients who do not live in a country where enrollment through an app is permitted, or who prefer to enroll through the CC, can initiate enrollment through the CC via phone or email using the contact details on the study website. After which, the CC research staff will contact potential patients to review the consent procedure and initiate enrollment. Future studies involving QUVIVIQ by Idorsia may provide information about this pregnancy registry and the process of referring any women who become pregnant. Patient or HCP reporting of pregnancy during exposure to QUVIVIQ for inclusion in the pregnancy registry is voluntary. HCPs will be made aware that any potentially eligible patients (either for Cohort A or Cohort B) should be referred to the registry as early as possible, ideally before prenatal testing has been performed. HCPs will also be made aware that any potentially eligible patients with retrospective pregnancies should be referred to the registry. Women with retrospective pregnancies who do not wish to enroll in the registry will be followed by Idorsia according to standard post-marketing pharmacovigilance.

5.4.5.1 Registry awareness

The registry will utilize awareness strategies that were effective in other pregnancy exposure registry programs. Multiple approaches, aimed toward both HCPs and patients, will be used to increase awareness of the registry, such as the study website, the website-associated app, social media, print and electronic media, and scientific conferences. The registry will also be included in labeling and listed on the US FDA Office of Women's Health Pregnancy Registry website. Registry awareness activities and content will be evaluated on a regular basis to ensure target populations are being reached yet minimize any burden on the recipients. Channels for providing feedback on registry

material and correspondence with potential HCPs and patients will be detailed in a Recruitment and Retention Plan.

5.4.5.2 Registry recruitment

Active outreach will occur to obtain reports of women exposed to QUVIVIQ during pregnancy and women with insomnia who may be eligible for the comparator cohorts and receive medical care from the same clinical sites. Outreach efforts may include the following:

- Discussion of the registry with investigators participating in QUVIVIQ clinical studies, with periodic written reminders.
- Notification of the registry to specialists and practitioners who may prescribe QUVIVIQ as well as insomnia education and support groups via the following:
 - Investigator awareness electronic flyer.
 - HCP introduction letters.
- Collection of patient referral information at enrollment (e.g., HCP, website/internet, sponsor, etc.)

Patient recruitment is dependent on several factors. The uptake of new medications like QUVIVIQ is unpredictable and has the potential to impact the feasibility of meeting recruitment targets. In addition, the expected pace of exposure to pregnant women and the willingness of pregnant women to voluntarily participate in a registry are difficult to predict. Continuous monitoring of patient recruitment rates (comparing projects with observed rates) will allow for strategies to be implemented in response to any recruitment challenges.

5.4.5.3 Registry retention

Registry retention efforts may include (but are not limited to) electronic newsletters to HCPs that may include engagement emails, SMS / text messages / email / phone call reminders, notifications through the website and associated app, or 'thank you' messages for patients and/or HCPs (where relevant). The projected vs observed dropout rates will be continuously monitored. Retention planning will be performed in advance as part of the Recruitment Risk Management Plan and will include steps to take if the rate of patient completion decreases. These steps to ensure patient recruitment and retention in the registry include an action plan to implement at study start, in addition to an action plan that may be implemented as the study progresses and new enrollment information becomes available. Retention efforts for both HCPs and patients will be documented in the Recruitment and Retention Plan.

Doc No D-23.335

5.4.6 Safety data collection

All AEs and SAEs following exposure to QUVIVIQ and in Cohort B will be recorded in the eCRF during the observation period from the LMP through the end of study follow-up (i.e., patient loss to follow-up, withdrawn consent, death [mother and/or infant], pregnancy termination, study termination, or end of the registry [whichever comes first]). HCPs will report maternal and fetal AEs and SAEs occurring during pregnancy and infant AEs and SAEs occurring during the infants first year of life as applicable to the CC research staff, who will enter them in the eCRF. All exposures to QUVIVIQ during pregnancy will be sent via the Idorsia pregnancy form to the Idorsia Drug Safety Department. Any AEs and SAEs following exposure to QUVIVIQ will also be reported to the Idorsia Drug Safety Department. See Section 7 for a full description of safety reporting procedures.

5.5 Study size

5.5.1 Sample size calculation for the primary outcome

The sample size (i.e., the number of enrolled patients) was calculated to ensure sufficient power to compare the prevalence of major congenital malformations in the infants of women exposed to QUVIVIQ (Cohort A) with infants of women exposed to other non-ORA medications for insomnia (Cohort B1) in the primary analysis using an NI testing approach with a one-sided significance level of $\alpha = 0.025$.

Hypothesis:

```
H_0: P_A- P_{B1} > margin versus H_1: P_A- P_{B1} < margin
```

where

P_A is the probability of major congenital malformations in Cohort A.

P_{B1} is the probability of major congenital malformations in Cohort B1.

The null hypothesis is that P_A is larger than P_{B1} by a margin corresponding to a risk ratio of 3.0:

```
Risk Ratio = (P_{B1} + margin) / P_{B1}
or margin = P_{B1}*Risk Ratio -P_{B1}
```

A general population prevalence of major congenital malformations of 3% among women in Cohort B1 is assumed. The NI margin is 3%*3.0–3%=6%.

Assuming a true difference of 0.15% between P_A and P_{B1} (corresponding to a relative increase of 5% from P_{B1}), sample sizes of 102 pregnancy outcomes in Cohort A and 204 events in Cohort B1 achieve 80.1% power to exclude an increase in risk of more than a risk ratio of 3 in Cohort A compared to Cohort B1. The test statistic used is the one-sided Z-test with a significance level of 2.5%. The proportion for the reference group is $P_{B1} = 3\%$

[see Table 3]. Calculations were made by using nQuery V9.1.1.0, module PTE0U-1 [Machin 1987].

The hypothesis testing will be based on comparing the upper bound of the 97.5% one-sided confidence interval for P_{A^-} P_{B1} with the NI margin. If the upper bound is below the NI margin, then noninferiority of A vs B1 will be concluded.

The following formula was utilized to calculate sample size:

$$Na = \frac{(r+1) * (Z_{1-\beta} + Z_{1-\alpha})^{2} * (\frac{Pa * (1-Pa) + Pb1 * (1-Pb1)}{2})}{r * ((Pa - Pb1) - margin)^{2}}$$

$$Nb1 = r * Na$$

where N_A is the number of pregnancy outcomes required in Cohort A, N_{B1} is the number of pregnancy outcomes required in Cohort B1, r is the allocation ratio (Cohort A: Cohort B1, 1:2 ratio), $Z_{1-\beta}$ and $Z_{1-\alpha}$ are the 80% and 97.5% percentiles of the standard normal distribution, respectively.

Sample size estimates with risk ratios varying from 2.0 to 3.0 and with various observed percentages in Cohort A are presented in Table 3.

These numbers are further adjusted with a 15% attrition rate (drop-out or missing data), a live birth rate of 62% [FDA 2002], and assuming that 5% of patients in Cohort A will be excluded from the primary analysis due to exposure to insomnia medications other than QUVIVIQ.

The calculation for the number of enrolled patients needed is as follows:

$$Enrolled\ patients = \sum_{i \in A, B1, B2} \frac{Pregnancy\ outcomes\ needed\ for\ each\ group_i}{Overall\ adjustment\ rate\ for\ each\ group_i}$$

For Cohort A the overall adjustment rate is as follows:

 $(1 - drop \ out \ rate \) \cdot (1 - proportion \ of \ pts \ with \ combined \ insomnia \ drugs) \cdot live \ birth \ rate = (1 - 0.15) \cdot (1 - 0.05) \cdot 0.62 = 0.50065.$

For Cohort B1 and B2 the overall adjustment rate is as follows:

$$(1 - drop \ out \ rate) \cdot live \ birth \ rate = (1 - 0.15) \cdot 0.62 = 0.527$$

The total number of enrolled patients needed in each cohort (Cohort A, Cohort B1 and Cohort B2, respectively) is as follows:

Number of enrolled patients =

$$\frac{102 (A)}{0.50065} + \frac{204 (B1)}{0.527} + \frac{102 (B2)}{0.527}$$
$$\approx 204 + 387 + 194 = 785$$

The number of enrolled patients needed depending on risk ratios varying from 2.0 to 3.0 and depending on expected prevalence of major congenital malformation in Cohort A are presented in Table 3.

 Table 3
 Sample size calculation

					nts to be enrolled ohort
Risk ratio	Assumed prevalence in Cohort B1	Expected prevalence of MCM in Cohort A ^a	NI margin corresponding to the risk ratio	Cohort A with 15% attrition rate, 62% live birth rate, and 5% exposure to insomnia medications other than QUVIVIQ	Cohort B1 with 15% attrition rate and 62%live birth rate
3.0	3.0%	3.0%	6%	192 (Pregnancy outcomes needed: 96)	362 (Pregnancy outcomes needed: 191)
3.0	3.0%	3.15%	6%	204 (Pregnancy outcomes needed: 102)	387 (Pregnancy outcomes needed: 204)
3.0	3.0%	3.3%	6%	218 (Pregnancy outcomes needed: 109)	414 (Pregnancy outcomes needed: 218)
2.75	3.0%	3.0%	5.25%	250 (Pregnancy outcomes needed: 125)	472 (Pregnancy outcomes needed: 249)
2.75	3.0%	3.15%	5.25%	268 (Pregnancy outcomes needed: 134)	509 (Pregnancy outcomes needed: 268)
2.75	3.0%	3.3%	5.25%	290 (Pregnancy outcomes needed: 145)	548 (Pregnancy outcomes needed: 289)

Confidential

					nts to be enrolled ohort
Risk ratio	Assumed prevalence in Cohort B1	Expected prevalence of MCM in Cohort A ^a	NI margin corresponding to the risk ratio	Cohort A with 15% attrition rate, 62% live birth rate, and 5% exposure to insomnia medications other than OUVIVIO	Cohort B1 with 15% attrition rate and 62%live birth rate
2.50	3.0%	3.0%	4.50%	340 (Pregnancy outcomes needed: 170)	643 (Pregnancy outcomes needed: 339)
2.50	3.0%	3.15%	4.50%	370 (Pregnancy outcomes needed: 185)	698 (Pregnancy outcomes needed: 368)
2.50	3.0%	3.3%	4.50%	401 (Pregnancy outcomes needed: 201)	761 (Pregnancy outcomes needed: 401)
2.25	3.0%	3.0%	3.75%	487 (Pregnancy outcomes needed: 244)	926 (Pregnancy outcomes needed: 488)
2.25	3.0%	3.15%	3.75%	537 (Pregnancy outcomes needed: 269)	1021 (Pregnancy outcomes needed: 538)
2.25	3.0%	3.3%	3.75%	595 (Pregnancy outcomes needed: 298)	1129 (Pregnancy outcomes needed: 595)
2.0	3.0%	3.0%	3.0%	761 (Pregnancy outcomes needed: 381)	1446 (Pregnancy outcomes needed: 762)
2.0	3.0%	3.15%	3.0%	857 (Pregnancy outcomes needed: 429)	1628 (Pregnancy outcomes needed: 858)
2.0	3.0%	3.3%	3.0%	971 (Pregnancy outcomes needed: 486)	1843 (Pregnancy outcomes needed: 971)

^a Expected prevalence in Cohort A is P_A = 1.0, 1.05, 1.10 · P_B, reflecting that the expected prevalence in Cohort A is slightly higher (increase of 0%, 5%, 10%) than the background prevalence in Cohort B.

MCM = major congenital malformation; NI = non-inferiority.

For the secondary analysis (comparison of the prevalence of major congenital malformations in the infants of Cohort A to the infants of Cohort B2), 194 pregnancy

Confidential

outcomes in Cohort B2 (1:1 ratio Cohort A:Cohort B2) would allow 86% power to rule out a difference represented by a risk ratio of 3.5 or higher in major congenital malformations at a significance level of $\alpha = 0.025$.

If the prevalence observed in Cohort A is lower than 3.15% (expected prevalence), there will be greater power to demonstrate that the rate of major congenital malformations in the infants of patients in Cohort A is not larger than in Cohort B1.

Subject recruitment will be evaluated at each interim review. Interim analyses are planned for the 5th year after the first patient enrolls, and annually thereafter [Section 5.1]. This will include a sample size re-estimation examining the observed prevalence and risk ratio of major congenital malformations in Cohort A compared with Cohort B1 and account for patient recruitment rates and enrollment projects.

Calculations were performed using nQuery version 9.1.1.0 and R version 4.2.2, using the epi.ssninfb function in the package epiR.

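### With about 3 and 6 expected events, the primary non-inferiority Z-test does not deliver its stated 2.5% error and 80.1% power: exact error is 5.1% to 5.7%, exact power 76.5% to 79.0%

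*Protocol*

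**What the plan says.** Section 5.5.1 of the protocol fixes the elements of the primary test:

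- **Reference prevalence:** "A general population prevalence of major congenital malformations of 3% among women in Cohort B1 is assumed".
- **True difference:** 0.15 points, "corresponding to a relative increase of 5% from" the Cohort B1 value, so 3.15% in Cohort A.
- **Margin:** "The NI margin is 3%*3.0–3%=6" per cent, matching a risk ratio of 3.0.
- **Test:** "The test statistic used is the one-sided Z-test with a significance level of 2.5" per cent. Non-inferiority is concluded when the upper 97.5% one-sided bound for P_A − P_B1 is below the margin.
- **Size and power:** "sample sizes of 102 pregnancy outcomes in Cohort A and 204 events in Cohort B1" are said to "achieve 80.1% power to exclude an increase in risk of more than a risk ratio of 3". The word for Cohort B1 must mean outcomes, as Table 3 shows.

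The section prints a sample size formula that uses the simple average of the two binomial variances and says it was the formula used. Table 3 lists 15 scenarios. No exact or small-sample check of error or power is given.

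**The concern.** A Z-test for a difference in proportions relies on the normal approximation. Here the expected counts are 102 × 0.0315 = 3.2 and 204 × 0.03 = 6.1. In that range the estimated standard error moves with the estimated difference: a chance low count in Cohort A lowers both, so the upper bound falls below the margin too easily.

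The claim at stake is the primary safety conclusion. A false conclusion would declare a tripling of major malformations excluded when it is not. The protocol sets that risk at 1 in 40. If the rule actually runs near 1 in 20, the stated level is wrong, and the stated power belongs to a test that does not hold its level.

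**Working it through.** **Inputs (section 5.5.1).** P_A = 0.0315, P_B1 = 0.03, margin 0.06, one-sided α = 0.025, target power 80%, r = 2. The distance to the margin is 0.06 − 0.0015 = 0.0585, and its square is 0.0034223. (1.960 + 0.842)² = 7.849.

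**Step 1: reproduce the plan's figure.** With the pooled variance, p̄ = (0.0315 + 2 × 0.03)/3 = 0.0305 and p̄(1 − p̄) = 0.02957.

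- N_A = 1.5 × 0.02957 × 7.849 / 0.0034223 = 101.73, so 102/204.
- At 102/204 the standard error is √[0.02957 × (1/102 + 1/204)] = 0.02085. Power = Φ(0.0585/0.02085 − 1.960) = Φ(0.845) = 80.1%, as stated.
- The same calculation matches 14 of the 15 rows of Table 3. The exception is risk ratio 2.5 with 3.15%, where it gives 184 against a printed 185.

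**Step 2: compare the printed formula.** The average variance is (0.0315 × 0.9685 + 0.03 × 0.97)/2 = 0.02980.

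- N_A = 1.5 × 0.02980 × 7.849 / 0.0034223 = 102.5, so 103 in Cohort A.
- Its power at 102/204 is 79.8%.
- An unpooled two-cohort variance gives 103.3 and 79.5%.

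The printed formula is therefore not the one behind Table 3, but the gap at the design row is one outcome in Cohort A.

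**Step 3: exact behaviour of the rule at 102/204.** Take every pair of event counts, apply the rule, and sum the binomial probabilities of the pairs that conclude non-inferiority. Error is evaluated at the margin (9% against 3%) and power at 3.15% against 3%.

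| Rule | One-sided error | Power |
|---|---|---|
| Stated in section 5.5.1 | 2.5% | 80.1% |
| Unpooled (Wald) bound | 5.1% | 76.5% |
| Pooled Z-test | 5.7% | 79.0% |
| Farrington-Manning score limit | 1.6% | 53.2% |

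**Step 4: dependence on the 3% assumption.** Hold the 6-point margin and vary P_B1 from 1% to 5%. The error runs from 6.7% down to 4.1% for the unpooled bound and from 8.0% down to 4.4% for the pooled test. Neither reaches 2.5% anywhere in that range.

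**Step 5: why the score limit costs so much power.** At the margin the true standard error is √(0.09 × 0.91/102 + 0.03 × 0.97/204) = 0.0308. The Step 1 calculation uses 0.0209. A limit that reflects the variance at the margin needs roughly 1.96 × 0.0308 = 0.060, which already exceeds the available distance of 0.0585.

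**Step 6: would a slightly larger sample help?** At 104/207 the unpooled bound has power 75.9% and error 4.9%. Its exact power stays above 80% only from about 115/230, where the error is still 4.8%. Score-limit power reaches 80% at roughly 165/330.

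**The case against.** **The figures are right.** A reader who applies the printed formula or an unpooled variance might infer that 80.1% and Table 3 are miscalculated. The documents do not support that. A pooled-variance Z-test is a standard choice and reproduces the stated power and 14 of 15 rows. What remains is a small documentation mismatch over which formula was used.

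**The interval method is not named.** Section 5.5.1 says Z-test and confidence bound without naming the construction, and section 5.7.1.2 leaves analysis details to the SAP, which is not shown. Other intervals behave differently: at 9% against 3% the error is 3.0% for Agresti-Caffo and 1.6% for Newcombe. So it cannot be said that the final analysis will certainly run at twice its level. This part of the objection stands. It does not rescue the protocol's own statement, because section 5.5.1 itself ties the Z-test, the 2.5% level and the 80.1% power together, and neither simple Z form delivers that combination.

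**The power loss is modest.** This is also true: 1 to 4 points, depending on the variance. The doubled error is the substantive part.

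**The primary analysis also uses a risk ratio.** Section 5.7.1.3 specifies a risk ratio with a one-sided 97.5% interval, and section 5.7.4.3 adds the comparison of the difference with the margin. But the hypotheses, decision rule and power in section 5.5.1 are all written for the difference, so the stated error and power must hold there.

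**The year-5 re-estimation.** One might infer that it will repeat the same approximation. Section 5.5.1 says only that it will examine observed prevalence, risk ratio and recruitment; it names no formula.

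**Conclusion.** The concern holds as an inadequate normal approximation, not as an arithmetic error. At 102/204 the rule in section 5.5.1 has a one-sided error of 5.1% (unpooled) or 5.7% (pooled) against a stated 2.5%, and power of 76.5% or 79.0% against 80.1%. The roughly doubled error does not depend on which simple Z variance is chosen, and error stays above 4% for reference prevalences from 1% to 5%.

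The result assumes independent binomial outcomes, the full 102 and 204 evaluable outcomes, and a Z-type test or bound as the protocol words it. A different interval named in the SAP could hold the level, but then 80.1% would not be its power.

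**What to change.** In section 5.5.1 (and the SAP):

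1. Name the confidence limit for P_A − P_B1, choosing one that holds 2.5% at these event counts, for example the Farrington-Manning score limit.
2. Replace 80.1% with the power of that method at 102/204 from exact enumeration or simulation: about 53% for the score limit.
3. State that the year-5 sample size re-estimation will use the same method.
4. Print the pooled-variance formula that produced Table 3 in place of the average-variance one, and check the single row that differs by one.

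Resizing to 104/207 on the unpooled formula is not worth doing, since it corrects neither the error nor the power of the bound.

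The cost is wording and a clearly lower stated power; restating needs no extra enrolment. If the sponsor wants 80% power with the score limit, about 165/330 outcomes are needed. With the protocol's own adjustment rates that is 165/0.50065 ≈ 330 women in Cohort A and 330/0.527 ≈ 626 in Cohort B1, against 204 and 387 now. That choice is separate from the correction.
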